3.3 Other Efficacy Endpoints

3.3.1 Other Endpoints for Part 1

- Achievement of:
 - clinical remission per PROs at Week 2, Week 4, Week 8 and Week 12
 - clinical remission per CDAI at Week 2, Week 4, Week 8 and Week 12
 - enhanced clinical response at Week 2, Week 4, Week 8 and Week 12
 - clinical response at Week 2, Week 4, Week 8 and Week 12
 - CR-100 at Week 2, Week 4, Week 8 and Week 12
 - clinical remission per PROs and endoscopic remission at Week 12
 - clinical remission per CDAI and endoscopic remission at Week 12
 - enhanced clinical response and endoscopic response at Week 12
 - corticosteroid use discontinuation for CD and endoscopic remission at Week 12 (population: ITT subjects taking corticosteroids for CD at Baseline)
 - corticosteroid use discontinuation for CD and enhanced clinical response at Week 12 (population: ITT subjects taking corticosteroids for CD at Baseline)
 - corticosteroid use discontinuation for CD and endoscopic response at Week 12 (population: ITT subjects taking corticosteroids for CD at Baseline)
 - corticosteroid use discontinuation for CD at Week 12 (population: ITT subjects taking corticosteroids for CD at Baseline)
 - $\geq 50\%$ reduction in the corticosteroid dose for CD from Baseline at Week 12 (population: ITT subjects taking corticosteroids for CD at Baseline)

- decrease in SES-CD > 50% from Baseline or endoscopic remission at Week 12, as scored by central reviewer
- SES-CD ≤ 2 at Week 12
- SES-CD ulcerated surface subscore of 0 at Week 12 in subjects with SES-CD ulcerated surface subscore ≥ 1 at Baseline, as scored by a central reviewer
- SES-CD ulcerated surface subscore ≤ 1 in each segment at Week 12 in subjects with a SES-CD ulcerated surface subscore ≥ 2 at Baseline, as scored by a central reviewer
- endoscopic response at Week 12 among subjects with SES-CD subscore of 3 in the narrowing component at Week 12, which was not present at Baseline
- endoscopic remission at Week 12 among subjects with SES-CD narrowing component subscore between 0 and 2 in all intestinal segments at Baseline
- endoscopic response at Week 12 among subjects with SES-CD narrowing component subscore between 0 and 2 in all intestinal segments at Baseline
- endoscopic response or endoscopic remission at Week 12 among subjects with SES-CD narrowing component subscore between 0 and 2 in all intestinal segments at Baseline
- Colonic and Ileal Global Histologic Disease Activity Score (CGHAS/IGHAS) histologic remission (defined as CGHAS/IGHAS score ≤ 2) at Week 12 in subjects with abnormal histology at Baseline
- $\geq 50\%$ reduction in draining fistulas at Week 12 (population: ITT subjects with draining fistulas at Baseline)
- resolution of draining fistulas at Week 12 (population: ITT subjects with draining fistulas at Baseline)
- at least 50% decrease from Baseline in the number of days with very soft or liquid stools (Type 6 or 7, per Bristol Stool Chart) during the last 7 days at Week 12
- IBDQ remission (IBDQ ≥ 170 points) at Week 4, Week 12
- IBDQ response (increase in IBDQ ≥ 16 points from Baseline) at Week 4, Week 12

- response in IBDQ fatigue item (increase of IBDQ fatigue item score ≥ 1) at Week 4, Week 12
- response in IBDQ Bowel Symptom domain (increase of IBDQ bowel symptom domain score ≥ 8) at Week 12
- increase in FACIT-Fatigue total score from baseline ≥ 7 at Week 12
- increase in FACIT-Fatigue total score from baseline ≥ 9 at Week 12
- increase in FACIT-Fatigue total score from baseline ≥ 11 at Week 12
- resolution of EIMs at Week 2, Week 4, Week 8 and Week 12 (population: ITT subjects with EIMs at Baseline)
- Occurrence of:
 - hospitalizations during the 12-Week Double-Blind Induction Period (Part 1)
 - CD-related surgeries during the 12-Week Double-Blind Induction Period (Part 1)
- Change from Baseline in:
 - IBDQ at Week 4, Week 12
 - individual IBDQ domain scores (bowel, emotional, social, systemic) at Week 4, Week 12
 - individual IBDQ item under Bowel Symptom domain (for Q1, Q5, Q9, Q13, Q17, Q20, Q22, Q24, Q26, and Q29) at Week 4, Week 12
 - Work Productivity and Activity Impairment Questionnaire-Crohn's Disease (WPAI-CD) at Week 4, Week 12
 - European Quality of Life 5 Dimensions 5 level version (EQ-5D-5L) at Week 4, Week 12
 - Short Form-36 (SF-36) at Week 4, Week 12
 - Crohn's Symptoms Severity Questionnaire (CSS) at Week 4, Week 12
 - fecal calprotectin (FCP) at Week 4, Week 12
 - high sensitivity C-reactive protein (hs-CRP) at Week 2, Week 4, Week 8 and Week 12
 - average daily AP score at Week 2, Week 4, Week 8 and Week 12
 - average daily very soft/liquid SF at Week 2, Week 4, Week 8 and Week 12

- average daily total SF at Week 2, Week 4, Week 8 and Week 12
- CDAI at Week 2, Week 4, Week 8 and Week 12
- SES-CD at Week 12
- CGHAS/IGHAS at Week 12 among subjects with abnormal histology at Baseline
- FACIT-F at Week 4 and Week 12

3.3.2 Other Endpoints for Part 2

Same efficacy endpoints as those listed in Part 1 (Section 3.1 and Section 3.2) are considered for Part 2 of the study. All the Part 2 efficacy endpoints are considered other endpoints and ranking of the endpoints is not applicable for Part 2.

3.3.3 Other Endpoints for Part 3

- Achievement of:
 - clinical remission per PROs at Week 16, Week 20 and Week 24
 - clinical remission per CDAI at Week 16, Week 20 and Week 24
 - enhanced clinical response at Week 16, Week 20 and Week 24
 - clinical response at Week 16, Week 20 and Week 24
 - CR-100 at Week 16, Week 20 and Week 24
 - Endoscopic response at Week 24
 - endoscopic remission at Week 24
 - clinical remission per PROs and endoscopic remission at Week 24
 - clinical remission per CDAI and endoscopic remission at Week 24
 - enhanced clinical response and endoscopic response at Week 24
 - corticosteroid use discontinuation for CD and clinical remission per PROs at Week 24 (population: ITT subjects taking corticosteroids for CD at Week 12)
 - corticosteroid use discontinuation for CD and clinical remission per CDAI at Week 24 (population: ITT subjects taking corticosteroids for CD at Week 12)

- corticosteroid use discontinuation for CD and endoscopic remission at Week 24 (population: ITT subjects taking corticosteroids for CD at Week 12)
- corticosteroid use discontinuation for CD and enhanced clinical response at Week 24 (population: ITT subjects taking corticosteroids for CD at Week 12)
- corticosteroid use discontinuation for CD at Week 24 (population: ITT subjects taking corticosteroids for CD at Week 12)
- corticosteroid use discontinuation for CD and endoscopic response at Week 24 (population: ITT subjects taking corticosteroids for CD at Week 12)
- $\geq 50\%$ reduction in the corticosteroid dose for CD from Baseline at Week 24 (population: ITT subjects taking corticosteroids for CD at Week 12)
- resolution of EIMs at Week 24 (population: ITT subjects with EIMs at Baseline or Week 12)
- decrease in SES-CD $> 50\%$ from Baseline or endoscopic remission at Week 24, as scored by central reviewer
- SES-CD ≤ 2 at Week 24
- SES-CD ulcerated surface subscore of 0 at Week 24 in subjects with SES-CD ulcerated surface subscore ≥ 1 at Baseline, as scored by a central reviewer
- SES-CD ulcerated surface subscore ≤ 1 in each segment at Week 24 in subjects with a SES-CD ulcerated surface subscore ≥ 2 at Baseline, as scored by a central reviewer
- CGHAS/IGHAS histologic remission (defined as CGHAS/IGHAS score ≤ 2) at Week 24 in subjects with abnormal histology at Baseline
- $\geq 50\%$ reduction in draining fistulas at Week 24 (population: ITT subjects with draining fistulas at Baseline)
- resolution of draining fistulas at Week 24 (population: ITT subjects with draining fistulas at Baseline or Week 12)

- at least 50% decrease in the number of days with very soft or liquid stools (Type 6 or 7, per Bristol Stool Chart) during the last 7 days at Week 24.
- Occurrence of:
 - hospitalizations due to CD during Part 3
 - hospitalizations during Part 3
 - CD-related surgeries during Part 3
- Change from Baseline in:
 - IBDQ at Week 24
 - WPAI-CD at Week 24
 - EQ-5D-5L at Week 24
 - CSS at Week 24
 - FACIT-F at Week 24
 - SF-36 at Week 24
 - FCP at Week 16, Week 24
 - hs-CRP at Week 16, Week 20 and Week 24
 - average daily AP score at Week 16, Week 20 and Week 24
 - average daily very soft/liquid SF at Week 16, Week 20 and Week 24
 - average daily total SF at Week 16, Week 20 and Week 24
 - CDAI at Week 16, Week 20 and Week 24
 - SES-CD at Week 24
 - CGHAS/IGHAS at Week 24 among subjects with abnormal histology at Baseline
- Time to:
 - clinical response
 - enhanced clinical response
 - clinical remission per PROs
 - clinical remission per CDAI
 - CR-100

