#### **5.3.3.2.2 Additional Efficacy Variables**

Non-ranked endpoints are as follows:

- Proportion of subjects:
  - with clinical remission per PROs over time
  - with clinical remission per CDAI (CDAI < 150) over time
  - with enhanced clinical response over time
  - with clinical response over time
  - with CR-100 over time
  - with clinical remission per PROs and endoscopic remission at Week 12
  - with clinical remission per CDAI and endoscopic remission at Week 12
  - with enhanced clinical response and endoscopic response at Week 12

- who discontinue corticosteroid use for CD and achieve endoscopic remission at Week 12, in subjects taking corticosteroids for CD at Baseline
- who discontinue corticosteroid use for CD and achieve enhanced clinical response at Week 12, in subjects taking corticosteroids for CD at Baseline
- who discontinue corticosteroid use for CD and achieve endoscopic response at Week 12, in subjects taking corticosteroids for CD at Baseline
- who discontinue corticosteroid use for CD at Week 12, in subjects taking corticosteroids for CD at Baseline
- with  $\geq 50\%$  reduction in the corticosteroid dose for CD from Baseline at Week 12, in subjects taking corticosteroids for CD at Baseline
- with hospitalizations during the 12 week double-blind induction period
- undergoing CD-related surgeries during the 12 week double-blind induction period
- decrease in SES-CD  $> 50\%$  from Baseline of the induction study or endoscopic remission at Week 12, as scored by central reviewer
- with SES-CD  $\leq 2$  at Week 12
- with SES-CD ulcerated surface subscore of 0 at Week 12 in subjects with SES-CD ulcerated surface subscore  $\geq 1$  at Baseline, as scored by a central reviewer
- with SES-CD ulcerated surface subscore  $\leq 1$  in each segment at Week 12 in subjects with a SES-CD ulcerated surface subscore  $\geq 2$  at Baseline, as scored by a central reviewer
- with endoscopic remission at Week 12 among subjects with SES-CD subscore of 3 in the narrowing component at Week 12, which was not present at Baseline
- with endoscopic response at Week 12 among subjects with SES-CD subscore of 3 in the narrowing component at Week 12, which was not present at Baseline
- with endoscopic response or endoscopic remission at Week 12 among subjects with SES-CD subscore of 3 in the narrowing component at Week 12, which was not present at Baseline

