9.0 Efficacy Analyses

9.1 General Considerations

The primary and secondary efficacy endpoints as specified in Section 3.0 will be analyzed based on ITT1 for Part 1. The difference between treatment groups for the primary and secondary efficacy endpoints will be tested with graphical multiplicity adjustment¹ to

ensure a strong control of family-wise type I error rate at significance level $\alpha = 0.05$ (2-sided) (see Section 12.0). Analyses of other efficacy endpoints for Part 1 will be performed using ITT1 at significance level $\alpha = 0.05$ (2-sided) without multiplicity adjustment.

No statistical comparisons will be performed for Part 2 and Part 3. For all efficacy endpoints, the descriptive statistics will be provided by treatment group for Part 1, for overall for Part 2 and by cohort for Part 3. The statistics include number of observations, mean, standard deviation, 95% CI, minimum, median, and maximum for continuous variables, and number, percent and two-sided 95% CI for discrete variables. And number of subjects with missing data due to COVID-19 pandemic will be summarized for primary and secondary efficacy endpoints.

Unless otherwise specified, any subject who is randomized based on a wrong stratum will be analyzed according to the actual stratum the subject belongs to.

The Primary Analysis will be performed after all enrolled subjects have completed Part 1, Part 2 and Part 3, and the database has been locked. This will be the only and final efficacy analysis.

"Baseline" refers to the last non-missing observation prior to the first administration of study drug in Part 1 or Part 2 or prior to the randomization if no study drug is given.

Analysis of Categorical Variables:

For categorical variables, frequencies and percentages will be reported for each treatment group in Part 1, for overall for Part 2 and for each cohort in Part 3. Comparison of upadacitinib group and placebo group will be performed using the Cochran Mantel-Haenszel (CMH) test adjusting for stratification factors (baseline steroid use (Yes, No), endoscopic disease severity ($SES-CD < 15, \geq 15$) and number of prior biologics with prior inadequate response or intolerance ($\leq 1, > 1$)). If there is a stratum for a treatment group that has no subject in it, a value of 0.1 will be added to all cells in the corresponding table in order to prevent dividing by 0, as suggested in Greenland and Robins (1985).² Point

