9.2.1 Categorical Endpoints

For binary efficacy endpoints other than the occurrence of hospitalization and the occurrence of CD-related surgery, missing data will be handled using the following approaches:

- The primary approach for handling missing data in the analysis of binary endpoints will use **Non-Responder Imputation (NRI)** while incorporating Multiple Imputation (MI) to handle missing data due to **COVID-19 (NRI-C)**.
 - The NRI-C will categorize any subject who does not have an evaluation during a pre-specified visit window (either due to missing assessment or due to early withdrawal from the study) as a non-responder for the visit. The only exception is that missing data due to COVID-19 infection or logistical restriction will be handled by MI. At each visit, subjects will be characterized as responders or non-responders based on MI imputed values if missing due to COVID-19; otherwise, subjects will be considered as non-responders for missing due to other reasons in the NRI-C approach. In addition, at and after the CD-related corticosteroids intercurrent event (see Section 8.2) and on/after the date of initiation of CD-related confounding medications after premature discontinuation of study drug (see Section 8.1), subjects will be considered as non-responders and will not be imputed by MI.

- A sensitivity analysis for binary endpoints will use **NRI** with **No** special data handling for missing due to **COVID-19** (NRI-NC).
 - NRI-NC will be performed in the same way as NRI-C without the exception above. Missing due to COVID-19 infection or logistical restriction will also be counted as non-responders. Subjects on or after the occurrence of the CD-related corticosteroids intercurrent event and on/after the date of initiation of CD-related confounding medications after premature discontinuation of study drug will still be considered as non-responders. This is the same method as "NRI" as defined in the protocol.
- Details on MI method in NRI-C are described below:

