9.4 Secondary Efficacy Analyses

9.4.1 Main Analyses of Ranked Secondary Efficacy Endpoints

The attributes of the estimands corresponding to the ranked secondary efficacy endpoints are summarized in [Table 2](#).

In general, continuous secondary efficacy variables with repeated measurements will be analyzed using a MMRM model including factors for treatment group, visit, visit by treatment interaction, and stratification variables. The MMRM analysis is considered primary for inferential purposes. Continuous secondary efficacy variables which are collected at only one post-baseline visit (such as SES-CD) will be analyzed using ANCOVA approach.

Categorical secondary efficacy variables will be analyzed using the CMH test controlling for stratification factors (baseline steroid use (Yes, No), endoscopic disease severity (SES-CD < 15, \geq 15) and number of prior biologics with prior inadequate response or intolerance (\leq 1, > 1)). A CMH based two-sided 95% CI for the difference between treatment groups will be constructed. NRI-C method for missing data will be used for categorical secondary endpoints except occurrence of hospitalizations due to CD during Part 1. The endpoints of "Occurrence of hospitalization due to CD during Part 1" will be analyzed using Chi-square test (or Fisher's exact test if \geq 20% of the cells have expected cell count < 5).

The NRI-C method will be the primary approach for missing data handling for categorical secondary endpoints except hospitalization due to CD during Part 1. The endpoint of "Occurrence of hospitalization due to CD during Part 1" will be analyzed based on the observed data using AO approach only.

Table 2. Summary of the Estimand Attributes of the Key Secondary Efficacy Endpoints

Attributes of the Estimand					
	Treatment	Endpoint	Population	Handling Intercurrent Events	Statistical Summary

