9.5 Additional Efficacy Analyses

Part 1

Other efficacy endpoints will be analyzed similarly as the secondary efficacy endpoints as described in Section 9.4. No multiplicity adjustment will be considered.

Part 2 and Part 3

Only descriptive statistics will be provided for the Part 2 and Part 3 endpoints specified in Section 3.3. The analyses for Part 2 will be performed using ITT2, and the analyses for Part 3 will be performed using the ITT3 by cohort. Categorical endpoints will be summarized by number, percent and two-sided 95% CI; and continuous endpoints will be summarized by n, mean, standard deviation, 95% CI, minimum value, median, and

maximum value; and time to response endpoints will be summarized by n, number of events, and the 25%, 50%, 75% percentiles of time (in days).

A programming error from the ed diary vendor was identified in the total number of daily stools question on patient ed diaries that does not allow the transaction to progress if the answer 0 to question 1, "How many stools in total have you had in the last 24 hours from last record until now?" The vendor has confirmed the issue was only present in languages that are translated from right to left. For this program, that includes Hebrew and Arabic in Israel and Egypt, respectively.

Since data from total stool frequency is only applicable to non-ranked additional efficacy endpoints, a sensitivity analysis will be performed for the additional efficacy endpoint of change from Baseline in average daily total stool frequency at all scheduled visits, by excluding subjects from Egypt and Israel.

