Appendix E. Simple Endoscopic Score – CD (SES-CD)

SES-CD is calculated based the sum of individual segment values for four endoscopic variables (presence and size of ulcers, ulcerated surface, affected surface and presence of narrowing). Each variable in each segment be scored 0 to 3 resulting in SES-CD values ranging from 0 to 56 with higher scores indicating more severe disease.

Variable	Score			
	0	1	2	3
Size of ulcers (cm)	None	Aphthous ulcers (diameter 0.1–0.5)	Large ulcers (diameter 0.5–2)	Very large ulcers (diameter >2)
Ulcerated surface (%)	None	<10	10–30	>30
Affected surface (%)	Unaffected segment	<50	50–75	>75
Presence of narrowings	None	Single, can be passed	Multiple, can be passed	Cannot be passed

* Total SES-CD: sum of the values of the 4 variables for the 5 bowel segments. Values are given to each variable and for every examined bowel segment (for example, rectum, left colon, transverse colon, right colon and ileum).

Medscape Source: Nat Rev Gastroenterol Hepatol ©2009 Nature Publishing Group

[figure not shown]
SES-CD Scoring:

	Rectum	Sigmoid and Left Colon	Transverse Colon	Right Colon	Ileum	Total
Size of Ulcers Enter: 0 if none 1 if aphthous ulcers (Ø 0.1 to 0.5 cm) 2 if large ulcers (Ø 0.5 to 2 cm) 3 if very large ulcers (Ø > 2 cm)						
Ulcerated Surface Enter: 0 if none 1 if < 10% 2 if 10% – 30% 3 if > 30%						
Affected Surface Enter: 0 if unaffected segments 1 if < 50% 2 if 50% – 75% 3 if > 75%						
Presence of Narrowing Enter: 0 if none 1 if single, can be passed 2 if multiple, can be passed 3 if cannot be passed						
					TOTAL =	

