Appendix I. Random Seeds

In case of non-convergence, the random seed will be updated by adding 100000 at each attempt until convergence of model happens.

Table I-1. Random Seeds for NRI-C

Variables	Random Seed	
	MCMC Procedure	PROC MI
CDAI	14431	24431
SES-CD (for 20 individual variables)	N/A	24432
SF	14441	24441
AP score	14451	24451
EIM	N/A	24452
IBDQ total score	14461	24461
FACIT-F	14471	24471
CGHAS	14491	24491

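### Endoscopic response among subjects with new impassable narrowing at Week 12 is tested between arms, although the subset is defined after randomisation and its membership is undefined when the endoscopy is missing

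*SAP*

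**What the plan says.** SAP Section 3.3.1 includes, among the other Part 1 endpoints, "endoscopic response at Week 12 among subjects with SES-CD subscore of 3 in the narrowing component at Week 12, which was not present at Baseline". Protocol Section 5.3.3.2.2 lists the same non-ranked variable, with the same condition that the narrowing be new since Baseline. SAP Appendix E defines the narrowing score: "3 if cannot be passed".

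The analysis comes from three general statements:

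- SAP Section 9.1: "Analyses of other efficacy endpoints for Part 1 will be performed using ITT1 at significance level" two-sided 0.05, without multiplicity adjustment.
- SAP Section 9.5: "Other efficacy endpoints will be analyzed similarly as the secondary efficacy endpoints as described in Section 9.4". Section 9.4.1 uses a CMH comparison of the arms. Section 9.1 replaces it with a chi-square or Fisher test when numbers are small, but the arms are still compared.
- SAP Section 9.4.1: "NRI-C method for missing data will be used for categorical secondary endpoints", with hospitalisation as the only exception.

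SAP Section 9.2.1 gives the missing-data rule: "The NRI-C will categorize any subject who does not have an evaluation during a pre-specified visit window" as a non-responder for that visit, except that COVID-19 missingness goes to multiple imputation. Nothing in the SAP makes this endpoint descriptive or gives it an estimand of its own.

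**The concern.** New impassable narrowing at Week 12 is something the drug may prevent, or may fail to prevent. Conditioning on it compares upadacitinib subjects who narrowed despite treatment with placebo subjects who narrowed without it. Randomisation balances the full ITT1 population. It does not balance these two groups unless treatment leaves membership unchanged. The neighbouring narrowing endpoints in Section 3.3.1 restrict on Baseline narrowing (0 to 2 in all segments) and do not have this problem.

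The second difficulty is the denominator. Membership and outcome are read from one endoscopy. If that endoscopy is missing, the rule that missing counts as non-response says what the outcome is, but not whether the subject belongs to the subset.

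At stake is one exploratory p-value or interval that could be read as a treatment effect in subjects who develop strictures.

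**Working it through.** **1. The plan's own figure.** SAP Section 2.4 claims at least 95% power with 330 and 165 subjects (Fisher's exact test, two-sided 0.05). Exact enumeration gives 98.7% for endoscopic response (10% vs 25%), 99.4% for PRO remission (12% vs 29%) and 99.6% for CDAI remission (20% vs 40%). The claim is reproduced, but it concerns the full ITT1. The plan states no figure for the narrowing subset and no rate of new narrowing, so everything in steps 2 to 5 rests on assumed rates.

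**2. Weak selection.** Assume a latent severity z, standard normal, and no drug effect on response given severity:

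- logit P(narrowing) = −3.6 + b·z + log(OR)·arm, with b from 1 to 2 and OR 0.3 or 0.5
- logit P(response) = −1.6 − z

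Integrating over z and scaling to 165 and 330 subjects, with CI half-width 1.96 × √[p₀(1−p₀)/n₀ + p₁(1−p₁)/n₁]:

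| b | OR | Placebo in subset | Upadacitinib in subset | Total | Spurious difference (points) | 95% CI half-width (points) |
|---|---|---|---|---|---|---|
| 1 | 0.3 | 6.7 | 4.3 | 11 | −0.4 | 36 |
| 1 | 0.5 | 6.7 | 7.0 | 14 | −0.25 | 32 |
| 2 | 0.3 | 14.6 | 12.4 | 27 | −1.0 | 18 |
| 2 | 0.5 | 14.6 | 18.1 | 33 | −0.6 | 17 |

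Only about one responder or fewer is expected per arm, so the half-widths are rough.

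**3. Stronger selection.** Again assume no drug effect on response. Suppose everyone who narrows on the arm with less narrowing would also narrow on the other. Let those who narrow on either arm respond at rate a, and those who narrow on one arm only respond at rate c. The arm with less narrowing (proportion q_low) shows a. The other arm (q_high) shows [q_low·a + (q_high − q_low)·c] / q_high. Differences are upadacitinib minus placebo.

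| Narrowing, placebo vs upadacitinib | a = 5%, c = 20% | a = 2%, c = 30% |
|---|---|---|
| 5% vs 5% | 0 | 0 |
| 5% vs 3% | 5 − 11 = −6 | 2 − 13.2 = −11.2 |
| 5% vs 1%, or 10% vs 2% | 5 − 17 = −12 | 2 − 24.4 = −22.4 |
| 2% vs 5% | 14 − 5 = +9 | 18.8 − 2 = +16.8 |

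Worked case, 5% vs 3%: placebo = (3 × 5% + 2 × 20%)/5 = 11%; upadacitinib = 5%.

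**4. What a test could detect.** Fisher power for 10% vs 25% within the subset:

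| New narrowing, both arms | Placebo / upadacitinib | Power |
|---|---|---|
| 1% | 2 / 3 | 0% |
| 2% | 3 / 7 | 0.1% |
| 5% | 8 / 16 | 1.3% |
| 10% | 16 / 33 | 14.8% |

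With 11 vs 10 subjects and 7% response in both arms, the chance of Fisher p < 0.05 is about 0.2%.

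**5. Unplaceable subjects.** If 5% to 20% lack a Week 12 endoscopy (assumed), that is 8 to 33 placebo and 16 to 66 upadacitinib subjects. This is of the same order as the subset, or larger.

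**6. Membership constrains the outcome.** One subscore of 3 makes the Week 12 SES-CD at least 3. A fall of more than 50% then needs a Baseline score of at least 7, since (6−3)/6 is exactly 50% and (7−3)/7 is 57%. The exception for a Baseline score of 4 needs a Week 12 score of 2 or less, so it cannot be met here.

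**The case against.** The endpoint is non-ranked, openly unadjusted and outside the procedure in SAP Section 12.0. The small-sample rule would probably send it to Fisher's test, and step 4 shows that a false positive is then very unlikely in at least one plausible configuration. All of this stands, and it limits the practical harm.

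Three stronger readings are tempting, and the documents do not support them.

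- **That NRI-C cannot be applied at all.** SAP Appendix I plans imputation of the 20 individual SES-CD variables (4 variables by 5 segments). These include narrowing, so membership could be imputed for COVID-19 missingness. The SAP does not describe the resulting denominator, which would vary across the 30 datasets. For other missing endoscopies, a literal reading of the endpoint simply leaves the subject out. The gap is that no rule is stated. The same gap arises after a corticosteroid intercurrent event, because Section 9.2.1 sets the measurements to missing before imputation.
- **That the sponsor recognised the flaw and overlooked this endpoint.** The Section 13.0 history for version 4.0 records deletion of the two sister endpoints. Remission requires no subscore above 1, so it is impossible with a subscore of 3, and remission-or-response then reduces to response. One deletion removed an impossible endpoint and the other a redundant one. Post-randomisation selection was not the reason given. Response alone remains attainable.
- **That the bias has a known size or direction.** Steps 2 and 3 differ by more than an order of magnitude, and the sign depends on which arm narrows more.

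**Conclusion.** The point holds as a minor one. The planned test conditions on a Week 12 finding that treatment may affect, taken from the same endoscopy as the outcome, so randomisation does not protect it. The non-responder step has no defined denominator when that endoscopy is missing for non-COVID reasons.

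The size of any bias is unknown. The illustrations give about 11 to 33 of 495 subjects under the weak-selection model, and spurious differences from under 1 point to about 20 points (−22 to +17 across the cases shown). They rest on assumed narrowing rates, an assumed severity distribution and assumed response rates by narrowing type. The bias vanishes if the same subjects would narrow under either treatment. At these sizes the test is nearly uninformative whatever the bias. The co-primary and ranked endpoints, the type I error procedure and the sample size are not touched.

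**What to change.** State in SAP Sections 3.3.1 and 9.5 that this endpoint is reported as counts by arm among subjects with an observed Week 12 endoscopy, with no p-value and no confidence interval for the difference. The same sentence should say how endoscopies after a corticosteroid intercurrent event are counted.

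Optionally, as a separate question, report by arm the ITT1 subjects with a new narrowing subscore of 3 at Week 12, showing those without a Week 12 endoscopy as their own category. This describes the incidence of new narrowing, not response despite narrowing. It needs that explicit category because counting missing as non-response has no clear meaning for an adverse finding.

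The cost is a few lines of SAP wording and one exploratory p-value.
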